Statistical methods	
Descriptive statistics were performed on the clinical data, and measures that conformed to normal distribution were expressed as mean±standard deviation ($\bar{x} \pm s$), and t-test was used between groups, and measures that did not conform to normal distribution were expressed as median (interquartile spacing) [M(IQR)], and Mann-Whitney U test was used between groups. Count data were expressed as percentages [n(%)], and the chi-square test was used for between-group comparisons, with $P<0.05$ considered statistically significant. The Kaplan-Meier method in STATA 12.0 was used to calculate the recurrence rate and recurrence-free survival in each group, and the log-rank test was used for intergroup comparison.

Duration of the study	24 months

catalogs

1. Research background	1
2. Research purpose	4
3. Types of Research Designs and Experimental Steps	4
4. Case selection	9
5. Research Methodology and Technical Approach.....	10
6. Observed items and testing time points	12
7. Criteria for evaluating the efficacy of treatment	13
8. Adverse Events Watch.....	14
9. Data security monitoring.....	16
10. Statistical processing	16
11. Ethical principles of clinical research.....	17
12. Reference	17

1. Research background

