(4) Clinical outcome collection: to collect clinical outcome indicators of subjects after surgery, such as: postoperative complication rate, recurrence rate, recurrence-free survival, quality of life.

5) Medical cost collection: to collect subjects' total hospitalization cost, cost of anti-infective drugs, cost of albumin during hospitalization.

Data analysis:

Descriptive statistics were performed on the clinical data, and the measures that conformed to normal distribution were expressed as mean \pm standard deviation ($\bar{x} \pm s$), and the t-test was used between the groups, and the measures that did not conform to normal distribution were expressed as median (interquartile spacing) [M(IQR)], and the Mann-Whitney U test was used between the groups. Count data were expressed as percentages [n(%)], and the chi-square test was used for between-group comparisons, with $P < 0.05$ considered statistically significant. The Kaplan-Meier method in STATA 12.0 was used to calculate the recurrence rate and recurrence-free survival in each group, and the log-rank test was used for intergroup comparison.

4. Case selection

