4.4 Exclusion criteria

Enrolled cases but meeting one of the following should be excluded:

- 1) Intraoperative exploration of the tumor has undergone dissemination or is unresectable;
- 2) Serious intraoperative or postoperative complications of surgical technique within 24h: bleeding or gastrointestinal leakage leading to shock;
- 3) Serious cardiac, pulmonary, cerebral or renal vital organ accidents or insufficiency during the operation or within 24h after the operation;
- 4) Postoperative pathology suggesting non-primary or metastatic hepatocellular carcinoma;
- 5) Patients in the control group who had more than 7 additional meals before bedtime;
- 6) Patients in the test group who did not have more than 7 bedtime refills during the follow-up period;
- 7) Those who voluntarily withdrew.

5. Research Methodology and Technical Approach

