5.1 Research Methodology

1) Nutritional Assessment

All patients were screened for nutritional risk using the NRS 2002 scale within 24 h of admission, and a score of ≥ 3 was considered to be at nutritional risk; patients at nutritional risk were assessed for nutrition using the PG-SGA scale and diagnosed with malnutrition according to the GLIM Malnutrition Assessment (Diagnosis) Criteria.

2) Nutritional support therapy

The target intake for all patients was 25-30 kcal/kg/d. Nutritional supportive therapy was given to patients who were at nutritional risk and could not achieve the target intake. Oral nutritional supplements were preferred, and enteral nutritional supplementation was used in patients who still could not achieve 60% of the target amount. Supplemental parenteral nutrition was considered if patients could not achieve 60% of the target amount for 7 days after admission to the hospital.

3) Interventions

From the total daily intake, patients in the test group were divided into approximately 250kcal for late-evening snacks 1h before bedtime (200-275kcal total, 11.5g-18g protein, 25-55g complex carbohydrates); patients in the control group did not eat any more food 1h before bedtime.

Preparations used:

- ① Enteral nutrition powder: 450kcal/15.9g/100g;
- ② Whole protein type enteral nutrition suspension, energy density 1kcal/ml, protein 0.05g/ml, complex carbohydrate 0.126g/ml;
- ③ Whey protein powder, protein content >80g/100g.

[figure not shown]
4) Biological sample collection

Post-test residual serum samples from patients on day 1 of admission, day 6 postoperatively, 1 month postoperatively, 3 months postoperatively, and 6 months postoperatively were collected for metabolomic analysis to see if the metabolic pattern of the patients was altered in LES mode.

5) Clinical outcomes

The postoperative complication rate, tumor recurrence rate, recurrence-free survival, postoperative hospitalization time, total hospitalization cost, and cost of anti-infective drugs of the subjects after admission to the hospital were counted, and the chi-square test and independent samples t-test were performed to compare the differences, in order to find out whether the clinical outcomes had been improved under the LES model.

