7.2 Clinical outcomes

1) Post-operative complications

a) Postoperative infections: surgical site infections (SSI), remote infections (RI) and bacteremia.

SSI: Shallow/deep incision SSI and organ/space SSI were defined as redness, swelling, heat, pain, and purulent discharge observed in any incision or space operated on intraoperatively, or the need for a new drain within 30 days postoperatively.

Distant infections: including cholangitis, enteritis, pneumonia, catheter-related infections, and urinary tract infections, defined as fever greater than 38.5°C, leukocytosis, and bacteria detected in

sputum, catheter tips, and urine and feces.

Bacteremia: Bacteremia is diagnosed when a strain is cultured from a single blood culture. And when the strain is identified as coagulase-negative staphylococci, it is considered contaminating; coagulase-negative staphylococci may be considered the causative agent when isolated from two or more blood cultures.

b) Bile leakage

Fluid with a bilirubin concentration of at least three times the serum bilirubin concentration drained through an abdominal drain on or after postoperative day 3. Regardless of the initial bilirubin concentration of the drain placed through surgery, the need for radiologic (i.e., interventional drainage) or surgical intervention (i.e., relative to cesarean section) for biliary collection or biliary peritonitis is also part of the diagnosis of bile leakage.

c) Liver failure after hepatectomy

Elevated serum bilirubin concentration and elevated INR on or after postoperative day 5 compared to the previous day; or coagulation factors such as fresh frozen plasma (FFP) are required to maintain normal INR values on or after postoperative day 5 in combination with hyperbilirubinemia.

- 2) Total hospitalization cost: the total cost of the patient from admission to discharge;
- 3) Recurrence-free survival: the time from the start of the patient's hepatectomy to the first detection of tumor recurrence;
- 4) Quality of Survival: Quality of Survival was evaluated by the EORTC QLQ - HCC18 scale (Appendix 1);
- 5) Safety, diarrhea, vomiting: complaints of gastrointestinal distress that occur after the patient has initiated nutritional support therapy, with diarrhea defined as unformed stools more than three times per day.

8. Adverse Events Watch

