Adverse events (AEs), all adverse medical events that occur after a subject receives a late-night snack, which can be manifested as symptoms signs, illnesses, or abnormal laboratory tests, but are not necessarily causally related to the late-night snacks.

Serious Adverse Event (SAE), an adverse medical event such as death, life-threatening, permanent or severe disability or loss of function, subject requiring hospitalization or prolonged hospitalization, and

congenital anomalies or birth defects that occur after a subject receives late-evening snacks.

The investigator will closely observe or follow up the various reactions of the patients after performing the LES in order to detect adverse events or serious adverse events in a timely manner, and all adverse events such as bloating, diarrhea, etc., reported by the subjects or observed by the investigator during the period from enrollment to the end of the study or early withdrawal from the study must be documented in the medical record or CRF, including laboratory and ancillary investigations, and should include, at a minimum, the name of the AE, its occurrence time (to the nearest minute), end time (to the nearest minute), degree and frequency of episodes, whether or not treatment was corrected, the course of treatment and regression if treatment was documented, and the causal relationship to the study. All medical documentation related to the adverse event must be recorded in the original documentation, including copies of requests for laboratory tests and reports of test results. The name of the investigator must be signed and dated (to the nearest minute) on the original documents and written reports.

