A data safety monitoring program will be established for clinical studies according to the level of risk. All adverse events will be recorded in detail, appropriately handled and followed up until properly resolved or stabilized, and serious adverse events and unintended events, etc., will be reported to the Ethics Committee, the competent authority, the sponsor, and the drug regulatory authority in a timely manner according to the regulations; the principal investigator will conduct a cumulative review of all adverse events on a regular basis, and convene a meeting of the investigators to assess the risks and benefits of the study, if necessary; the injuries or discomfort is no more likely and no greater in magnitude than that encountered in daily life or than that of a routine examination, and that data and safety monitoring can be accomplished by the principal investigator.

10. Statistical processing

应用 SPSS26.0 统计软件对临床数据进行描述性统计，符合正态分布的计量资料以均数±标

准差($\bar{x} \pm s$)表示, 组间采用 t 检验, 不符合正态分布的计量资料以中位数(四分位间距) [M(IQR)] 表示, 组间采用 Mann-Whitney U 检验。计数资料用百分比[n(%)]表示, 组间比较采用卡方检验, $P<0.05$ 为有显著性统计学意义。采用 STATA12.0 中的 Kaplan-Meier 法计算各组复发率及无复发生存期, log-rank 检验进行组间比较。SPSS26.0 statistical software was applied to carry out descriptive statistics of the clinical data, and the measurements that conformed to normal distribution were expressed as mean \pm standard deviation ($\bar{x} \pm s$), and t-test was used between the groups, and the measurements that did not conform to normal distribution were expressed as median (inter-quartile spacing) [M(IQR)], and Mann-Whitney U-test was used between the groups. Count data were expressed as percentages [n(%)], and the chi-square test was used for between-group comparisons, with $P<0.05$ considered statistically significant. The Kaplan-Meier method in STATA 12.0 was used to calculate the recurrence rate and recurrence-free survival in each group, and the log-rank test was used for between-group comparisons.

11. Ethical principles of clinical research

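### Recurrence-free survival is defined so that a death without recurrence is never an event, and section 5.1 lists it under chi-square and t-tests while the rest of the plan uses Kaplan-Meier and log-rank

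*Combined protocol and SAP*

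**What the plan says.** Section 7.2, item 3, holds the only definition of the endpoint: "Recurrence-free survival: the time from the start of the patient's hepatectomy to the first detection of tumor recurrence". The synopsis lists it among the secondary efficacy indicators, and section 6.5 schedules its follow-up at 1, 3 and 6 months after surgery.

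Two methods are given for it:

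- **Section 5.1, item 5 (Clinical outcomes).** A list that begins "The postoperative complication rate, tumor recurrence rate, recurrence-free survival, postoperative hospitalization time, total hospitalization cost" is followed by the statement that "the chi-square test and independent samples t-test were performed to compare the differences". No other method is named there.
- **Synopsis (Statistical methods), section 3.2 (Data analysis) and section 10.** Kaplan-Meier "was used to calculate the recurrence rate and recurrence-free survival in each group". For the comparison, the synopsis and section 3.2 say "the log-rank test was used for intergroup comparison", and section 10 says "the log-rank test was used for between-group comparisons".

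Section 4.4 lists reasons for removing patients after enrolment. They include specified serious events during surgery or within 24 hours and "Those who voluntarily withdrew". Death is not on the list. Section 3.2 puts patient survival on the data form without naming a date of death.

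**The concern.** Readers take recurrence-free survival to mean alive and free of recurrence. Under 7.2, item 3, a patient who dies without recurrence, for example from the liver failure or infections that 7.2 itself defines, is never counted as a failure. The result would be time to recurrence reported as RFS, and a difference in deaths between the arms would not show in it. No other named endpoint captures mortality, although the primary purpose in section 2.1 includes long-term prognosis.

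The definition also makes two listed outcomes the same. If recurrence is the only event and both quantities come from Kaplan-Meier, the recurrence rate is one minus RFS. The second adds information only if death counts.

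The second problem is the conflict over the test. Neither a chi-square test nor a t-test on follow-up times handles censoring, and the plan does not say which passage governs.

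**Working it through.** **What the plan's own figures cover.** The documents give no event rate, hazard ratio or required number of events for RFS, so there is no RFS figure to reproduce. The sample size in section 3.1 is for albumin. With a difference of 37.5 − 34.2 = 3.3 g/L and SD √((3.9² + 5.4²)/2) = 4.71, an exact two-sided t-test at 0.05 has 90.1% power with 44 per group, which agrees with the plan's 88. The plan's 53 per group equals 44 × 1.2 = 52.8, rounded up. Only the arm sizes 44 and 53 are used below.

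**Assumptions (not in the documents).** By 6 months, cumulative incidence of recurrence R is 15% or 25%, and of death without recurrence D is 1%, 3% or 5%. Hazards are constant. Deaths are treated as censored, because the plan gives them no other status.

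**Formulas.**
- RFS with death counted = 1 − R − D
- Kaplan-Meier on the 7.2 definition = (1 − R − D)^(R/(R + D))

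| R | D | RFS, death counted | Kaplan-Meier, 7.2 definition | Excess (points) |
|---|---|---|---|---|
| 15% | 1% | 84.0% | 84.9% | 0.9 |
| 15% | 3% | 82.0% | 84.8% | 2.8 |
| 15% | 5% | 80.0% | 84.6% | 4.6 |
| 25% | 1% | 74.0% | 74.9% | 0.9 |
| 25% | 3% | 72.0% | 74.6% | 2.6 |
| 25% | 5% | 70.0% | 74.3% | 4.3 |

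Example: 0.80^(0.15/0.20) = 0.80^0.75 = 0.846.

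**If all deaths come before any recurrence.** Kaplan-Meier then gives 1 − R/(1 − D). At R = 25%, D = 1% this is 1 − 0.25/0.99 = 74.75% against 74.0%, an excess of 0.75 points. At R = 15%, D = 5% it is 1 − 0.15/0.95 = 84.2% against 80.0%, an excess of 4.2 points. Over both timings the excess is about 0.8 to 4.6 points.

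**Scale.** One uncounted death is 1/53 = 1.9 points, or 1/44 = 2.3 points. The standard error of a 6-month RFS of 80% in 53 patients is √(0.8 × 0.2/53) = 5.5 points.

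**Recurrence rate taken as one minus Kaplan-Meier.** This exceeds the cumulative incidence R by 0.1 to 0.7 points with constant hazards, and by 0.2 to 1.3 points with early deaths.

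**The test conflict.** I simulated 53 per arm with no true difference, R = 15% or 25%, and losses of 20/20, 15/25 or 10/30% (6,000 runs per setting). When lost patients were removed, the t-test rejected in 4.4-6.5% of runs; log-rank rejected in 4.6-5.0%. The t-test fails clearly only when losses are unequal and lost patients are kept with truncated times: 10.9-13.4% at 15/25 and 30.5-38.5% at 10/30. Section 4.4 does not keep withdrawals in that way, so no inflated error rate is claimed.

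**The case against.** **The definition is silent on death rather than excluding it.** It is true that no passage says deaths are censored. But a rule that ends the clock only at detected recurrence leaves no way for a death to be an event, and no other passage supplies one.

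**The 0.8 to 4.6 points compare two different endpoints.** If time to recurrence is what is wanted, the error is only the 0.1 to 1.3 points in the recurrence rate, and renaming the endpoint would cure the label. This is fair, and renaming with an explicit rule for deaths is a legitimate alternative. It would leave mortality outside every named endpoint.

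**The rates are assumed and the excess is a shift within an arm.** This stands. Eligibility limits and the 24-hour removals in 4.4 may keep deaths few. If deaths are balanced, the comparison between arms changes little.

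**Section 5.1, item 5, is a loose summary.** Probably so: it gives a mixed list and does not match tests to outcomes, while three other places name Kaplan-Meier and log-rank for these two. That makes it an inconsistency to remove, and nothing more is claimed.

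**Deaths will be known anyway.** Survival is on the form, and section 8 asks for all adverse events from enrolment to the end of the study. However, section 8 defines them as "Adverse events (AEs), all adverse medical events that occur after a subject receives a late-night snack", so cover of the control arm is unclear, and no date of death is named on the form.

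**Conclusion.** The concern holds on both parts. The endpoint in 7.2, item 3, is time to recurrence under an RFS label, with no rule for deaths without recurrence or for patients lost without formally withdrawing. Section 5.1, item 5, contradicts the synopsis, section 3.2 and section 10 on the method.

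The true size is unknown. The overstatement of about 0.8 to 4.6 points in 6-month RFS rests wholly on the assumed rates and on deaths being censored; it stays below one standard error and vanishes if nobody dies without recurrence. RFS is secondary, unpowered and followed to 6 months, and albumin is untouched. The definition should be corrected before analysis, but it does not threaten the main result.

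**What to change.** 1. In 7.2, item 3, define RFS as time from hepatectomy to first recurrence or death from any cause, whichever comes first. Censor event-free patients at their last recurrence assessment.
2. In 5.1, item 5, remove recurrence rate and RFS from the chi-square and t-test sentence, so that Kaplan-Meier and log-rank is the only method for RFS.
3. If recurrence rate is still reported separately, estimate it by cumulative incidence with death as a competing event, and amend the synopsis, section 3.2 and section 10, which now take both quantities from Kaplan-Meier.
4. Confirm that dates of death and of last recurrence assessment are recorded in both arms.
5. Check the censoring rule against 4.4, which removes patients who withdraw.

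Items 1 and 2 cost a few lines and need no extra patients or visits. Item 3 adds one analysis for a small gain (0.1 to 1.3 points under the same assumptions). Items 4 and 5 are checks of the data form and of the text.

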	
his/her supplementation must be completed before 1h before bedtime.
 
2. Biological sample collection:
 
The remaining post-test serum samples need to be collected for metabolomics analysis from patients on day 1 of admission, postoperative day 6, postoperative 1 month, postoperative 3 months, and postoperative 6 months.
 
3. Clinical data collection:
 
1) General information: gender, age, height, weight, BMI, ICG 15min retention time, name of surgery, duration of surgery, blood loss, blood transfusion, tumor stage, NRS2002, GLIM malnutrition assessment (diagnostic) criteria diagnosis.
 
2) Nutritional indicators: Nutritional indicators such as serum albumin (ALB), prealbumin (PA), transferrin (TRF), and total serum protein (TP) were collected from patients on the 1st day of admission, the 6th postoperative day, 1 month postoperatively, 3 months postoperatively, and 6 months postoperatively.
 
(3) Liver function indexes: Liver function indexes such as alanine aminotransferase(ALT), alanine transaminase(AST), γ-glutamyltransferase (GGT), cholinesterase (CHE), and total bilirubin (TBIL) were collected on the 1st day of admission, the 6th postoperative day, 1 month postoperatively, 3 months postoperatively, and 6 months postoperatively.
 
(4) Clinical outcome: collect the patients' postoperative clinical outcome indicators, such as: postoperative complication rate, recurrence-free survival, and quality of survival.
 
(5) Medical costs: collect the total cost of the patients' hospitalization, the cost of anti-infective drugs, and the cost of albumin during hospitalization.

Evaluation of the	
Indicators of effectiveness evaluation
 
Main efficacy indicators: serum albumin (ALB)
 
Secondary efficacy indicators: serum prealbumin (PA), alanine

efficacy of treatment	aminotransferase (ALT), azelaic transaminase (AST), cholinesterase (CHE), total bilirubin (TBIL), total hospitalization costs, relapse-free survival, and quality of life
	
Safety evaluation indicators
 
Incidence of gastrointestinal symptoms such as abdominal distension, diarrhea, nausea and vomiting, incidence of postoperative complications, and length of postoperative hospitalization

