All patients were screened for nutritional risk using NRS 2002, nutritional assessment using PG-SGA, and malnutrition diagnosis using GLIM Malnutrition Assessment (Diagnosis) Criteria within 24h of admission. In accordance with the recommendations of ESPEN 2021 Practice Guidelines for Surgical Nutrition Therapy and CSPEN 2016 Guidelines for Perioperative Nutritional Support for Adults, the patients' daily target amount was set at 25-30 kcal/kg. In order to ensure the balanced dietary nutritional intake of the two groups, their standardized management was formulated as follows: ① Total calories: according to the patients' height, weight, age and activity Total calories: Calculate the daily intake according to the patient's height, weight, age and activity intensity, about 1200~2000 kcal. ② Carbohydrates: account for 60%~65% of the actual energy supply, calculate the actual supply of 180~325

g. The staple food is mainly cereals and potatoes. Protein: 1.2~1.5 g/kg/day according to the guideline, choose high quality protein, such as eggs, poultry, soybean products. ④Fat: account for 20% of the actual energy supply, calculate the actual supply of about 27~44 g. Distribute the energy of three meals as 30%, 40%, 30%. According to each patient's required intake, the corresponding nutritional program card is issued, and explained and emphasized at the time of admission and discharge, respectively. Patients could choose different food items on the cards according to their food preferences and actual situation. The experimental group was required to consume LES 1 h before bedtime, while the control group did not consume any food 1 h before bedtime.

Experimental group: patients were given additional meal (total calories 200-275kcal, protein 11.5g-18g, complex carbohydrates 25-55g) 1h before bedtime. the LES regimen was: ① whole protein type enteral nutrition; ② whey protein powder + bread or cookie. The addition of meals was carried out 1h before bedtime. The dietary regimen of the experimental group will be deducted from the corresponding late-evening snacks intake.

(1) Preoperative: ① Patients without nutritional risk: independent intake according to the issued diet program card. ② Patients with nutritional risk: daily oral whole-protein enteral nutrition on the basis of general diet after admission.

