(2) Postoperative: start drinking small amount of water on the 1st postoperative day, over to liquid diet after ventilation, and may over to autonomous semi-liquid diet + oral whole protein enteral nutrition during the day + LES program on the 2nd postoperative day. As the patient's voluntary intake meets 60% of the body's needs, the daytime oral enteral nutrition support can be gradually stopped and the LES program can be continued.

3) Discharge: daily intake needs to be on time according to the LES regimen.

Control group: no more food 1h before bedtime.

(1) Preoperative: same as the test group.

(2) Postoperative: start drinking small amount of water on the 1st postoperative day, over to liquid diet after ventilation, and can over to autonomous semi-liquid diet + oral whole protein type enteral nutrition during the day on the 2nd postoperative day. As the patient's voluntary intake meets 60% of the body's needs, enteral nutrition support can be gradually stopped.

(3) Discharge: Doctors judge whether the patients need to continue nutritional support according to their dietary recovery, and if they do, their nutritional supplementation should be completed before 1h

before bedtime.

2. biological sample collection:

Serum samples remaining after testing were collected from patients for metabolomics analysis.

3.Clinical information collection:

(1) General information collection: gender, age, height, weight, BMI, ICG15min retention time, name of surgery, duration of surgery, blood loss, blood transfusion, tumor stage, NRS2002, PG-SGA, GLIM malnutrition assessment (diagnosis) criteria diagnosis;

(2) Nutritional indicators collection: collect nutritional indicators such as serum albumin (ALB), prealbumin (PA), transferrin (TRF), and total serum protein (TP) on the 1st day of the subject's admission to the hospital, on the 6th day of the postoperative period, at 1 month after the operation, at 3 months after the operation, and at 6 months after the operation.

(3) Collection of liver function indexes: Liver function indexes such as alanine aminotransferase (ALT), alanine grass aminotransferase (AST), γ -glutamyltransferase (GGT), cholinesterase (CHE), and total bilirubin (TBIL) were collected on the first day of hospitalization, the sixth postoperative day, the first postoperative month, the third postoperative month and the sixth postoperative month of the subjects.

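### The gastrointestinal safety count opens when nutritional support starts, so its window depends on nutritional risk as well as on the snack

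*Combined protocol and SAP*

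**What the plan says.** The synopsis lists as a safety indicator "Incidence of gastrointestinal symptoms such as abdominal distension, diarrhea, nausea and vomiting". The operational definition is in section 7.2, item 5, which counts "complaints of gastrointestinal distress that occur after the patient has initiated nutritional support therapy". It gives no end to the counting period.

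The start of nutritional support is described in two places.

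- **Section 3.2, before surgery.** "Patients with nutritional risk: daily oral whole-protein enteral nutrition on the basis of general diet after admission". For the rest: "Patients without nutritional risk: independent intake according to the issued diet program card". The control group's entry reads "Preoperative: same as the test group".
- **Section 3.2, after surgery.** Test patients "may over to autonomous semi-liquid diet + oral whole protein enteral nutrition during the day + LES program on the 2nd postoperative day". Controls can have "oral whole protein type enteral nutrition during the day on the 2nd postoperative day". Neither sentence depends on nutritional risk, and both are permissive.
- **Section 5.1, item 2.** "Nutritional supportive therapy was given to patients who were at nutritional risk and could not achieve the target intake".

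Section 3.2 also allows the snack itself to be whole-protein enteral nutrition. The plan does not say whether the snack is nutritional support for the purpose of the count. Section 8 defines adverse events as those after a late-night snack, yet asks for all of them to be documented, with time of onset, from enrollment. Section 3.1 makes grouping non-randomized and by patient wish. Section 10 compares counts by an unadjusted chi-square test.

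**The concern.** An incidence is comparable between patients only if all are watched over the same period. Here the period opens at a point set by baseline nutritional risk.

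Take two patients who each vomit once on the evening of surgery and have no later symptoms. One was at risk and had enteral nutrition from admission, so the complaint counts. The other was not at risk and starts support on postoperative day 2, so it does not. Neither has reached the postoperative step at which the snack is listed. If section 5.1 governs, a patient who is not at risk may never start the count, and the same complaint on day 4 is also lost.

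Because patients choose their group, the share at nutritional risk can differ between groups. Part of that difference would then appear as a difference in gastrointestinal tolerance.

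**Working it through.** The plan states no gastrointestinal rate, at-risk share or counting period, so there is no figure of its own to reproduce. What follows is an illustration.

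**Inputs.** From the plan: 53 patients per group, and a chi-square test at the two-sided 5% level. Assumed: probability v of a complaint before postoperative day 2 = 30% (range 20–40%); probability l of a complaint from day 2 on = 20% (range 10–30%). The two are independent of each other and unrelated to group, risk status or snack. Share at risk r = 30% v 50%.

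**Step 1: who counts under section 3.2.**
- At risk: 1 − (1 − v)(1 − l) = 1 − 0.70 × 0.80 = 44% (range 28–58%).
- Not at risk: l = 20% (range 10–30%).

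**Step 2: group incidence under section 3.2**, r × 0.44 + (1 − r) × 0.20.
- r = 30%: 0.132 + 0.140 = 27.2%.
- r = 50%: 0.220 + 0.100 = 32.0%.
- False difference 4.8 points (range 2.8–7.2). Exact calculation with 53 per group gives 8.7% rejection. With equal shares of 30% it is 5.3%, so there is no meaningful excess.

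**Step 3: section 5.1, snack not counted as support.** If every at-risk patient misses target intake and starts at admission, incidence is r × 0.44.
- r = 30%: 13.2%. r = 50%: 22.0%. Difference 8.8 points (range 5.6–11.6), rejection 22.0%.
- Section 5.1 also requires failure to reach target intake, so these are upper limits at the assumed rates. If half of at-risk patients miss target: 0.30 × 0.5 × 0.44 = 6.6% v 0.50 × 0.5 × 0.44 = 11.0%. That is 4.4 points, with 12% rejection.

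**Step 4: section 5.1, snack counted as support.** Among patients not at risk, only those in the test group now start the count. With r = 50% in both groups and every at-risk patient started:
- Test: 0.5 × 0.44 + 0.5 × 0.20 = 32%.
- Control: 0.5 × 0.44 = 22%.
- Difference 10 points (range 5–15) with equal risk shares and no snack effect.

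**Step 5: a second model as a check.** Let incidence be 1 − (1 − h)^days, with daily risk h of 1–5%, 7 days counted from postoperative day 2, and for at-risk patients a further 2–7 preoperative days plus the day of surgery and day 1. For h = 2% and 4 preoperative days this gives 1 − 0.98^13 = 23.1% at risk against 1 − 0.98^7 = 13.2% not at risk. Over the whole range, a 20-point gap in risk share under section 3.2 gives a false difference of 0.7–5.2 points. If the snack doubles daily risk from day 2, with 50% at risk in each group, the indicator moves by 6.1–20.0 points.

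**The case against.** A reader might infer that the indicator follows nutritional risk and not the snack. The documents do not support that. Under section 3.2 daytime enteral nutrition is listed from postoperative day 2 in both groups whatever the risk status, with the snack added in the test group. Both groups are therefore being counted when the listed snack starts, and complaints it causes are captured. Risk status adds earlier counting time and does not replace the snack signal, as the last line of the working shows.

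The start rule is also the same in both groups under section 3.2, so equal at-risk shares mean no between-group bias. That stands. An imbalance is plausible with self-selected groups, but the plan does not show that one will occur.

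Nor should a start on day 2 and no start at all be read as one rule. The first comes from section 3.2 and the second from section 5.1, and the two conflict. The 8.8 points and 22% should not be taken as the section 5.1 result, because they ignore the target-intake condition.

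Finally, section 8 already asks for timed recording from enrollment, and albumin, not this indicator, is the primary endpoint. Both are true and limit the seriousness. But section 7.2 still decides which recorded complaints count, and section 8's definition begins at a snack that controls do not receive.

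**Conclusion.** The concern holds in a limited form. The stated rule gives patients different counting windows according to nutritional risk, so identical complaints can be scored differently. Whether this distorts the group comparison depends on which section governs:

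- **Section 3.2:** only if the at-risk shares differ. The illustration gives 4.8 points and about 9% rejection.
- **Section 5.1, snack not support:** again only if the shares that start support differ. At most 8.8 points and 22% at the assumed rates, less if some at-risk patients reach target intake.
- **Section 5.1, snack counted as support:** even with equal risk shares, 32% v 22%.

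All rates and shares are assumptions, so the size is uncertain. The dependence of the window on nutritional risk comes from the text itself. Even with no bias between groups, the reported incidence would mix different counting periods. This should be corrected for a named safety indicator. It does not affect the primary endpoint.

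**What to change.** Reword section 7.2, item 5, so that gastrointestinal complaints are counted in every patient of both groups over one common window, with a fixed start (for example postoperative day 2) and a fixed end, whether or not nutritional support was given. Tabulate earlier complaints separately. Do not label them pre-exposure unless the protocol confirms that no snack is given before surgery: section 3.2 states the bedtime meal in general terms ahead of its preoperative and postoperative items, so this is not clear.

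State that the section 8 recording from enrollment applies to controls as well. State whether the snack is nutritional support. Reconcile sections 3.2, 5.1, 7.2 and 8 on when support starts and for whom; which patients receive support is for the clinical team, and this change concerns counting only.

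The cost is a few sentences. No new data are needed, provided the section 8 recording is carried out in controls too. The small downside is that early complaints leave the main safety count for a separate table.
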